### 7.1.2. Exclusion Criteria

A patient will not be eligible for participation in this study if *any* of the following criteria apply.

1. Limited-stage SCLC
2. Prior chemotherapy for limited or extensive-stage SCLC
3. Prior treatment with immunotherapies including but not limited to cluster of differentiation 137 (CD137) agonists or immune checkpoint blockade therapies (such as anti-PD-1, anti-PD-L1, CTLA4 therapeutic antibodies)
4. Presence of symptomatic brain metastases requiring immediate treatment with radiation therapy or steroids
5. Malignancies other than SCLC within 3 years prior to randomization, with the exception of those with a negligible risk of metastasis or death treated with expected curative outcome
6. History of idiopathic pulmonary fibrosis, organizing pneumonia, drug induced pneumonitis, idiopathic pneumonitis, or evidence of active pneumonitis on screening chest CT scan (history of radiation pneumonitis in the radiation field [fibrosis] is permitted)
7. Active, known, or suspected autoimmune disease that has required systemic treatment in the past 2 years (ie, with use of disease modifying agents, corticosteroids, or immunosuppressive drugs). Exceptions include vitiligo, controlled asthma, type I diabetes, Graves' disease, Hashimoto's disease, or with medical monitor approval. Stable replacement therapy (eg, thyroxine, insulin, or physiologic corticosteroid replacement therapy for adrenal or pituitary insufficiency, etc.) for well-controlled disease is not considered a form of systemic treatment.
8. Uncontrolled ischemic heart disease or uncontrolled symptomatic congestive heart failure (Class III or IV as defined by the New York Heart Association [NYHA] functional classification system)
9. Known history of stroke or cerebrovascular accident within 6 months prior to enrollment
10. Serious active infection at the time of enrollment
11. Psychiatric illness/social situations that would limit study compliance
12. Other uncontrolled serious chronic disease or conditions that in the investigator's opinion could affect compliance or follow-up in the protocol
13. Known human immunodeficiency virus (HIV), known active Hepatitis B (eg, HBsAg reactive or HBV DNA detected) or Hepatitis C (eg, HCV RNA [qualitative] is detected)

14. Radiotherapy to any site within 2 weeks prior to enrollment
15. Receipt of any investigational medication within 4 weeks prior to enrollment
16. Administration of a live attenuated vaccine within 4 weeks before enrollment or anticipation that such a live attenuated vaccine will be required during the study
17. Influenza vaccination should be given during influenza season only (approximately October to March). Patients must not receive live, attenuated influenza vaccine (eg, FluMist) within 4 weeks prior to enrollment, at any time during the study, and at least 5 months after the last dose of atezolizumab
18. Patients with a condition requiring systemic treatment with either corticosteroids (> 10 mg daily prednisone equivalents) or other immunosuppressive medications (including but not limited to cyclophosphamide, azathioprine, methotrexate, thalidomide, and anti-tumor necrosis factor [TNF] agents) within 14 days of study drug administration. Inhaled or topical steroids and adrenal replacement doses > 10 mg daily prednisone equivalents are permitted in the absence of active autoimmune disease.
19. Hypersensitivity to any of the components of the formulation of etoposide or etoposide phosphate
20. Hypersensitivity to carboplatin or other platinum-containing compounds, or mannitol
21. History of severe allergic, anaphylactic, or other hypersensitivity reactions to chimeric or humanized antibodies or fusion proteins
22. Known hypersensitivity to Chinese hamster ovary cell products or other recombinant human antibodies
23. Legal incapacity or limited legal capacity
24. Pregnant or lactating women

Patients may withdraw from study drug or from the study at their own discretion (or at the discretion of the investigator) for any reason at any time (see Section [12.3](#) and [12.4](#)).

## 8. TREATMENTS

### 8.1. Treatments Administered

In the induction part of the study, patients will receive trilaciclib 240 mg/m^2 or placebo administered IV once daily on Days 1 to 3 of each 21-day E/P/A therapy cycle (up to 4 cycles in total). In the maintenance part of the study, patients will receive atezolizumab every 21 days.

Patients will receive E/P/A therapy in 21-day cycles during the induction part of the study. The carboplatin dose will be calculated using the Calvert formula with a target AUC = 5 (maximum 750 mg) IV over 30 minutes on Day 1, and 100 mg/m^2 etoposide will be administered IV over 60 minutes daily on Days 1, 2, and 3 of each 21-day cycle. Atezolizumab 1200 mg in 250 mL sodium chloride solution 0.9% will be administered as an IV infusion on Day 1 of each 21-day cycle in both the induction and maintenance parts. Atezolizumab should be infused over 60 minutes for the first administration and, if tolerated, all subsequent infusions may be delivered over 30 minutes. Atezolizumab should be administered following the completion of administration of trilaciclib or placebo, etoposide, and carboplatin.

There will be no inpatient dose modifications of trilaciclib or atezolizumab during the study. Dose modifications allowed for E/P are described in Section 8.4.5.

**The interval between doses of trilaciclib or placebo on successive days should not be greater than 28 hours. The interval between the dose of trilaciclib or placebo and the first dose of chemotherapy on a given day (etoposide or carboplatin) should not be greater than 4 hours.**

**Trilaciclib or placebo will only be administered with E/P therapy. If administration of E/P therapy is held or discontinued, trilaciclib or placebo will also be held or discontinued.**

**Chemotherapy cannot be administered until after completion of the trilaciclib or placebo infusion. If the second or third dose of trilaciclib or placebo in any given cycle is not administered for any reason, do not administer the dose of etoposide chemotherapy on that day, since this could potentially exacerbate myelosuppression (see Section 4.5).**

In both parts of the study, study drug administration will continue until disease progression per RECIST v1.1, unacceptable toxicity, withdrawal of consent, or discontinuation by investigator. Following disease progression per RECIST v1.1, if the patient appears to be deriving clinical benefit, the investigator believes it is in the best interest of the patient, and the patient has provided re-consent, study drug administration may be continued until loss of clinical benefit (see Section 11.1.4). Treatment cycles will occur consecutively without interruption, except when necessary to manage toxicities or for up to a 2-week delay for administrative reasons; however, a total delay of more than 9 weeks for trilaciclib or placebo +E/P, or 15 weeks for atezolizumab must be discussed with the medical monitor. If the subsequent cycle is delayed, the patient should still complete the clinical laboratory

assessments [REDACTED] on the scheduled Day 1, as well as on the actual first dosing day of the next cycle.

Patients should meet the requirements outlined in Section 6.1.1 before initiation of Cycle 2 and each subsequent induction cycle of therapy.

## 8.2. Investigational Products

Study drug refers to trilaciclib or placebo + E/P/A during the induction part and atezolizumab during the maintenance part.

### 8.2.1. Identity

#### 8.2.1.1. Trilaciclib

Trilaciclib is supplied as a single-use, sterile powder with 300 mg trilaciclib in each 30-mL flint glass vial. D-mannitol, USP is added as a cake forming agent and citrate buffer is added to maintain the reconstituted pH at 4.0 to 5.0. The process for reconstitution of study drug is detailed in the Pharmacy Manual.

#### 8.2.1.2. Placebo

The placebo formulation of 250 mL of dextrose 5% in water (D5W) or sodium chloride solution 0.9% will be prepared by the pharmacist/designee on site.

#### 8.2.1.3. Etoposide and Carboplatin

Descriptions of the formulations of commercially-available etoposide and carboplatin can be found in the respective current prescribing information (see [Appendix 4](#)).

#### 8.2.1.4. Atezolizumab

A description of the formulation of atezolizumab can be found in the current prescribing information (see [Appendix 2](#)).

### 8.2.2. Packaging and Labeling

#### 8.2.2.1. Trilaciclib

Trilaciclib Sterile Powder, 300 mg per vial is manufactured and packaged by [REDACTED].

Individual vials of trilaciclib will be labeled and supplied to the unblinded pharmacist/designee who will inventory the contents and document them according to the drug accountability requirements (Section 8.2.5).

#### 8.2.2.2. Placebo

The placebo formulation of 250 mL of D5W or sodium chloride solution 0.9% will be prepared by the pharmacist/designee on site, and labeled with the randomization number.

#### 8.2.2.3. Etoposide and Carboplatin

Descriptions of the packaging and labeling of commercially-available carboplatin and etoposide can be found in the respective current prescribing information (see [Appendix 4](#)).

#### 8.2.2.4. Atezolizumab

A description of the packaging and labeling of atezolizumab can be found in the current prescribing information (see [Appendix 2](#)).

### 8.2.3. Storage

#### 8.2.3.1. Trilaciclib

Study drugs will be stored [REDACTED] under applicable storage conditions at the site and only the pharmacist/designee and designated personnel will have access to the study drugs. Storage conditions of trilaciclib are detailed in the pharmacy manual.

#### 8.2.3.2. Placebo

The placebo formulation of 250 mL of D5W or sodium chloride solution 0.9% will be stored identically to trilaciclib to protect the integrity of the blind.

#### 8.2.3.3. Etoposide and Carboplatin

Information regarding the storage of commercially-available carboplatin and etoposide can be found in the respective current prescribing information (see [Appendix 4](#)).

#### 8.2.3.4. Atezolizumab

Information regarding the storage of atezolizumab can be found in the current prescribing information (see [Appendix 2](#)).

### 8.2.4. Procedure for Dispensing

Dispensing instructions, including instructions for masking the trilaciclib or placebo infusion bags and tubing will be provided in the Pharmacy Manual and will be maintained in the pharmacy records.

### 8.2.5. Investigational Product Accountability

The pharmacist/designee will verify the integrity of the clinical trial supplies (storage conditions, correct amount received, condition of shipment, kit numbers, etc.) according to the investigative site's standard operating procedures (SOPs).

At a minimum, the following data will be tracked on the drug accountability log at the site pharmacy:

- Date received
- Lot number

- Vial number
- Date dispensed
- Patient number
- Identification of the person dispensing the drug

Records of study medication (used, lost, destroyed, and returned containers, individual vials) should be made at each visit in the drug accountability and dispensing forms. Drug accountability and reconciliation will be checked and verified by the pharmacy team during the study and by the site monitor during and at the completion of the study.

Once the site monitor has verified drug accountability at the site, any used drug remaining at the completion of the study will be destroyed. Unused and unopened study medication will be returned by the site monitor to the sponsor or may be destroyed on site according to the investigative site's SOPs.

### **8.3. Method of Assigning Patients to Treatment Groups**

A unique patient identification number (screen number) will be assigned to each patient who signs an informed consent form. Patients meeting all inclusion and exclusion criteria will be randomized 1:1 to receive trilaciclib or placebo with E/P/A therapy during the induction part as described in Section 8.5. Each enrolled patient will be assigned a unique randomization number by an interactive web-response system (IWRS); this number will be unique and will not be reused.

### **8.4. Dose, Dosing Regimen, and Route**

#### **8.4.1. Trilaciclib**

Trilaciclib 240 mg/m^2 diluted in 250 mL of D5W or sodium chloride solution 0.9% is to be administered by IV infusion over approximately 30 minutes. If there is any study drug remaining in the infusion bag at the end of the 30 minutes, the infusion should be continued at the same rate until the entire contents of the bag have been administered to ensure patients receive the full dose. Details regarding the reconstitution and dilution of trilaciclib vials are detailed in the Pharmacy Manual.

**The interval between doses of trilaciclib on successive days should not be greater than 28 hours. Trilaciclib will only be administered with E/P therapy. If administration of E/P therapy is held or discontinued, trilaciclib will also be held or discontinued.**

#### **8.4.2. Placebo**

The placebo formulation of 250 mL of D5W or sodium chloride solution 0.9% will be administered over approximately 30 minutes. If there is any volume remaining in the infusion bag at the end of the 30 minutes, the infusion should be continued at the same rate until the entire contents of the bag have been administered to ensure patients receive the full dose.

**The interval between doses of placebo on successive days should not be greater than 28 hours. Placebo will only be administered with E/P therapy. If administration of E/P therapy is held or discontinued, placebo will also be held or discontinued.**

### 8.4.3. Etoposide and Carboplatin

Etoposide and carboplatin will be administered IV in accordance with the prescribing information (see [Appendix 4](#)) and according to the study site's standard practice.

Needles or IV administration sets containing aluminum parts that may come in contact with carboplatin should not be used for the preparation or administration of the drug. Aluminum can react with carboplatin causing precipitate formation and loss of potency.

**The interval between the dose of trilaciclib or placebo and the first dose of chemotherapy on a given day (etoposide or carboplatin) should not be greater than 4 hours.**

**Chemotherapy cannot be administered until after completion of the trilaciclib or placebo infusion. If the second or third dose of trilaciclib in any given cycle is not administered for any reason, do not administer the dose of etoposide chemotherapy on that day, since this could potentially exacerbate myelosuppression (see [Section 4.5](#)).**

#### 8.4.3.1. Carboplatin

The carboplatin dose will be calculated using the Calvert formula with a target AUC = 5 on Day 1 of each 21-day cycle and administered as an IV infusion over 30 to 60 minutes (per institutional standard of care). The Calvert formula is as follows:

$$\text{Total carboplatin dose (mg)} = (\text{target AUC}) \times (\text{GFR} + 25)$$

Because the estimated GFR may be based on serum creatinine measurements obtained using standardized isotope dilution mass spectrometry, the **dose of carboplatin should be capped at 750 mg** to avoid potential toxicity due to overdosing. The cap dose of 750 mg for carboplatin is based on a GFR estimate that is capped at 125 mL/min for patients with normal renal function (ie, maximum carboplatin dose = target AUC of 5 mg•min/mL × 150 mL/min = 750 mg).

The weight used for calculation of GFR using the Cockcroft-Gault equation should be the actual body weight (and not ideal body weight).

Refer to the carboplatin prescribing information (see [Appendix 4](#)) for details regarding preparation, administration, instructions and precautions. Premedications may be provided per local standard of care.

#### 8.4.3.2. Etoposide

Etoposide 100 mg/m^2 will be administered as an IV infusion over 60 minutes on Days 1, 2, and 3 of each 21-day cycle.

Refer to the etoposide prescribing information (see [Appendix 4](#)) for details regarding preparation, administration, instructions, and precautions.

#### 8.4.4. **Atezolizumab**

Atezolizumab 1200 mg will be administered as an IV infusion on Day 1 of each 21-day cycle. The first dose should be administered over 60 minutes and, if it is tolerated, subsequent doses may be administered over 30 minutes. For the first 4 cycles, ie, during the induction part, atezolizumab should be administered following the administration of trilaciclib or placebo, etoposide and carboplatin.

Refer to the atezolizumab prescribing information (see [Appendix 2](#)) for details regarding preparation, administration, instructions, and precautions.

#### 8.4.5. **Dose Modifications**

##### 8.4.5.1. Trilaciclib

To ensure the greatest level of safety when trilaciclib is coadministered with chemotherapeutic agents, the magnitude and duration of trilaciclib-induced HSPC arrest was simulated using a PK/pharmacodynamic model and verified by performing bone marrow cell cycle analysis before or after administration of trilaciclib IV at 192 mg/m^2 to different groups of human subjects in the Phase 1a Study G1T28-1-01. Trilaciclib at a dose of 192 mg/m^2 (rounded to 200 mg/m^2 for this study) demonstrated robust bone marrow HSPC arrest for > 24 hours and was determined to be the BED (Section 4.3.1). It is unknown if lower doses will produce the same magnitude and duration of HSPC cell cycle arrest. Insufficient HSPC arrest (ie, for too short a duration) could result in the release of HSPCs into the S (DNA synthesis) phase of the cell cycle while chemotherapy is present, thereby potentially exacerbating myelosuppression. However, higher doses of trilaciclib (240 and 280 mg/m^2) have been tested in patients with SCLC. Based on the Phase 1b results from these subsequent Phase 1b/2a SCLC studies (G1T28-02 [administered prior to etoposide and carboplatin] and G1T28-03 [administered prior to topotecan]), trilaciclib 240 mg/m^2 was chosen as the recommended Phase 2 dose. **Therefore, to minimize this risk of an insufficient HSPC arrest, the dose of trilaciclib will not be modified and will remain at 240 mg/m^2 throughout the study.**

##### 8.4.5.2. Modification of Etoposide and Carboplatin Dosing

Patients should meet the laboratory parameter requirements outlined in Section 10.3.2 before initiation of Cycle 2 and each subsequent cycle of E/P therapy. All nonhematologic drug-related toxicities (except alopecia) should have resolved to Grade 1 or baseline before initiation of the next cycle of E/P therapy.

Dose adjustments are to be made according to the organ system showing the greatest degree of drug-related toxicity. Toxicities will be graded using NCI CTCAE, Version 4.03. Initiation of the next cycle of trilaciclib or placebo + E/P therapy may be delayed by no more than 9 weeks to allow recovery from toxicity due to the chemotherapy agents. A treatment delay of > 9 weeks due to trilaciclib or placebo + E/P toxicity will lead to discontinuation of trilaciclib or placebo + E/P therapy.

No more than 2 dose reductions of E/P in total are allowed for any patient. Simultaneous reduction in the doses of etoposide and carboplatin will count as 1 dose reduction. Toxicity

that requires dose reduction more than twice will lead to discontinuation of trilaciclib or placebo + E/P therapy. Under this circumstance, administration of trilaciclib or placebo should also be discontinued. All dose reductions are permanent and no dose increases are allowed.

Since fatigue can be a symptom of cancer progression, dose reduction will only be performed if it is deemed to be drug-related in the opinion of the investigator.

The dose reductions in [Table 8-1](#) will be utilized for the purpose of dose modifications for toxicity.

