Atezolizumab has been associated with risks such as the following: infusion-related reactions (IRRs); immune-related hepatitis, pneumonitis, colitis, pancreatitis; diabetes mellitus; hypothyroidism; hyperthyroidism; adrenal insufficiency; Guillain-Barré syndrome; myasthenic syndrome or myasthenia gravis; hypophysitis; and meningoencephalitis. In addition, systemic immune activation is a potential risk associated with atezolizumab when given in combination with other immunomodulating agents. Refer to the Atezolizumab Guidance for the Investigator ([Appendix 1](#)) for a detailed description of anticipated safety risks for atezolizumab and their management.

Management of immune-related adverse events (irAEs) attributed to atezolizumab may include administration of immunosuppressant medications like corticosteroids, etc.; delay of a scheduled dose; or discontinuation of therapy. No dose reductions will be allowed for atezolizumab. Atezolizumab dosing will be held in the event of any irAEs attributed to atezolizumab until the event has improved to  $\leq$  Grade 1. See the Atezolizumab Guidance for the Investigator ([Appendix 1](#)).

Other irAEs attributed to atezolizumab not listed above should be assessed by the investigator and discussed with the medical monitor to determine if atezolizumab should be held or discontinued. If the irAE does not improve to  $\leq$  Grade 1 within 12 weeks, treatment will be permanently discontinued.

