### 6.1.1. Criteria for Subsequent Cycles and Study Duration

Study drug administration will continue for up to 4 chemotherapy-containing (trilaciclib or placebo + E/P/A) cycles during the induction part of the study and atezolizumab will be administered every 21 days during the maintenance part of the study. Study drug administration will continue until disease progression per Response Evaluation Criteria in Solid Tumors, Version 1.1 (RECIST v1.1), unacceptable toxicity, withdrawal of consent, or discontinuation by investigator, whichever occurs first. However, if the patient appears to be deriving clinical benefit, the investigator believes it is in the best interest of the patient, and the patient has provided re-consent, study drug administration may be continued until loss of

clinical benefit (see Section 11.1.4). Treatment cycles will occur consecutively without interruption, except when necessary to manage toxicities or for administrative reasons as described below.

In order to start Cycle 2 and subsequent cycles in the induction part up to Induction Cycle 4 as scheduled, patients should meet all of the following criteria:

- ANC  $\geq 1.5 \times 10^9/L$
- Platelet count  $\geq 100 \times 10^9/L$
- Nonhematologic drug-related toxicities (except alopecia) must be  $\leq$  Grade 1 or have returned to baseline

A delay of  $> 9$  weeks for recovery from any toxicity related to trilaciclib or placebo + E/P in order to meet the continuation criteria will result in discontinuation of trilaciclib or placebo + E/P. A delay of  $> 15$  weeks for recovery and management of immune-related toxicities attributed to atezolizumab (12 weeks for recovery to  $\leq$  Grade 1 and up to an additional 3 weeks for steroid taper of oral prednisone or equivalent to  $\leq 10$  mg/day) will result in discontinuation of atezolizumab (see Section 8.4.5.3). If patients meet the criteria for starting the subsequent cycle, a delay of up to 2 weeks is permitted for administrative reasons (eg, holiday, vacation, etc.); however, a total delay of more than 9 weeks for trilaciclib or placebo + E/P, or 15 weeks for atezolizumab must be discussed with the medical monitor. [REDACTED]

[REDACTED]

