### Dose Modifications for Hematologic Toxicity

#### First Day of Induction Cycle 2 and Beyond

In order to start Induction Cycle 2 and subsequent induction cycles as scheduled, on Day 1 of the cycle, patients must have an ANC  $\geq 1.5 \times 10^9/L$ , platelet count  $\geq 100 \times 10^9/L$ , and nonhematologic drug-related toxicities (except alopecia) must be  $\leq$  Grade 1 or have returned to baseline. The dose adjustments in [Table 8-2](#) are based on the ANC and platelet counts on the first day of treatment for Cycle 2 and each subsequent induction cycle.

**Table 8-2 Etoposide and Carboplatin Dose Adjustments Based on Lack of Recovery of Absolute Neutrophil or Platelet Counts on the First Day of Induction Cycle 2 and Each Successive Cycle**

Absolute Neutrophil Count <math>< 1.5 \times 10^9/L</math>	Etoposide	Carboplatin
First episode	No change. Use G-CSF with subsequent cycles. Refer to the American Society of Clinical Oncology (ASCO) guidelines (Smith 2015).	No change. Use G-CSF with subsequent cycles. Refer to ASCO guidelines (Smith 2015).
Second episode	First dose reduction	First dose reduction
Third episode	Second dose reduction	Second dose reduction
Fourth episode	Discontinue drug	Discontinue drug
Platelet Count <math>< 100 \times 10^9/L</math>	Etoposide	Carboplatin
First episode	First dose reduction	First dose reduction
Second episode	Second dose reduction	Second dose reduction
Third episode	Discontinue drug	Discontinue drug

G-CSF = granulocyte colony-stimulating factor

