If corticosteroids have been initiated as part of the irAE management, they must be tapered over  $\geq 1$  month to  $\leq 10$  mg/day oral prednisone or equivalent before atezolizumab can be resumed. If the delay for re-starting atezolizumab is  $> 15$  weeks for recovery from immune-related toxicities attributed to atezolizumab (12 weeks for recovery to  $\leq$  Grade 1 and up to an additional 3 weeks for steroid taper of oral prednisone or equivalent to  $\leq 10$  mg/day), atezolizumab will be permanently discontinued.

**Discontinuation or interruption of trilaciclib or placebo + E/P does not preclude continuation of atezolizumab and vice versa. For instance, if an AE is attributed to trilaciclib or placebo, etoposide, or carboplatin (eg, hematologic toxicity) during the induction part of the study, then atezolizumab will be continued while the trilaciclib or placebo + E/P are held. While the trilaciclib or placebo + E/P are held, the patient will continue to receive atezolizumab, be monitored for safety (see Section 10.3.4), and will begin the next trilaciclib or placebo + E/P/A-containing induction cycle after the toxicity resolves. If the AE is immune related and attributed to atezolizumab; then trilaciclib or placebo + E/P will be continued for up to 4 induction cycles while the atezolizumab is held.**

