#### 10.3.4. **Atezolizumab Administration While Trilaciclib or Placebo + E/P Is Held**

During the induction part, interruption or delay of trilaciclib or placebo + E/P does not preclude continuation of atezolizumab and vice versa. If the AE is immune related and attributed to atezolizumab, then trilaciclib or placebo + E/P will be continued for up to 4 cycles while atezolizumab is held. If an AE is attributed to trilaciclib or placebo, etoposide, or carboplatin (eg, hematologic toxicity) during the induction part of the study, then atezolizumab will be continued every 21 days while trilaciclib or placebo + E/P are held. During the period in which trilaciclib or placebo + E/P are held and atezolizumab is continued, patients should be monitored as follows prior to administering atezolizumab every 21 days:

- ECOG performance status evaluation
- Physical examination
- Weight and vital signs measurements
- Clinical chemistry, hematology, and urinalysis tests (note: clinical chemistry and urinalysis tests may be obtained up to 72 hours prior to the first dose of each cycle of study treatments, and hematology tests may be obtained up to 24 hours prior to the first dose of each cycle of study treatments). The clinical chemistry and hematology results should be reviewed before dosing.
- FACT-L and FACT-An Questionnaires

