Discontinuation or interruption of trilaciclib or placebo + E/P does not preclude continuation of atezolizumab and vice versa. For instance, if an AE is attributed to trilaciclib or placebo, etoposide, or carboplatin (eg, hematologic toxicity) during the induction part of the study; then atezolizumab may be continued while the trilaciclib or placebo + E/P are held. While the trilaciclib or placebo + E/P are held, the patient will continue to receive atezolizumab, be monitored for safety, and will begin the next trilaciclib or placebo + E/P/A-containing induction cycle after the toxicity resolves. If the AE is immune related and attributed to atezolizumab; then trilaciclib or placebo + E/P may be continued for up to 4 cycles while the atezolizumab is held.

After discontinuation of all study drugs, patients should be strongly encouraged to complete all scheduled assessments through the end of their current 21-day treatment cycle, [REDACTED]; CBC assessment on Day 22; all Post-Treatment Visits; and the Survival Follow-up Phase of the study, which is to continue until at least 70% of the patients on the study have died. The G1T28-05 study will be completed when the Survival Follow-up Phase has been completed, or upon sponsor termination of the study.

- The total study duration is at least 36 months, assuming 12 months of accrual and 24 months follow-up.
- The Survival Follow-up Phase will continue until at least 70% of the randomized patients have died.

The study scheduled assessments are presented in [Table 2](#) below:

Table 2 Schedule of Assessments

Cycle Day	Screening	Enroll	Induction (21-day cycles) ^a										Last Induction Cycle	Maintenance (21-day cycles) ^b		Post-Treatment Visits ^c		Survival Follow-up ^d
			Induction Cycles 1 and 3					Induction Cycles 2 and 4						Maintenance Cycle 1 and Odd Cycles	Maintenance Cycle 2 and Even Cycles	30 (+3)	90 (+7)	
	-14	-3 to 1	1	2	3	8	15	1	2	3	8	15	22	1	1	30 (+3)	90 (+7)	
Informed Consent ^e	X																	
Demographics	X																	
Medical History ^f	X																	
Eligibility Eval.	X	X																
Performance Status	X		X					X						X	X	X	X	
Physical Exam	X		X					X						X	X	X	X	
Height, Weight & Vital Signs ^g	X		X		X			X		X				X	X	X	X	
Electrocardiogram	X												X					
Clinical Chemistry	X		X ^h					X ^h						X ^h	X ^h	X	X	
TSH, free T4, and free T3	X							X							X	X	X	
Hematology	X		X ⁱ		X	X	X	X ⁱ		X	X	X	X	X ⁱ	X ⁱ	X	X	
Urinalysis	X		X ^h					X ^h						X ^h	X ^h	X	X	

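### For a nonhematologic atezolizumab immune event above Grade 1 and above baseline during induction, the plan tells sites both to continue E/P and to wait, and does not say which rule prevails

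*Protocol*

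**What the plan says.** **Rule to wait.** Protocol 8.4.5.2 makes the next E/P cycle conditional on recovery: "All nonhematologic drug-related toxicities (except alopecia) should have resolved to Grade 1 or baseline before initiation of the next cycle of E/P therapy". The list in 6.1.1 has the same condition ("Nonhematologic drug-related toxicities (except alopecia) must be" at Grade 1 or less, or back at baseline). It recurs in 8.4.5.2 under First Day of Induction Cycle 2 and Beyond ("nonhematologic drug-related toxicities (except alopecia) must be", same threshold), in the Synopsis, in 10.3.2 and 10.3.3, and in the SAP's text on criteria for subsequent cycles. No version restricts the condition to toxicity of particular drugs.

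**Rule to continue.** For an immune-related event attributed to atezolizumab, Protocol 8.4.5.3 says "then trilaciclib or placebo + E/P will be continued for up to 4 induction cycles while the atezolizumab is held". Section 10.3.4 says "then trilaciclib or placebo + E/P will be continued for up to 4 cycles while atezolizumab is held". The Synopsis, 6.1.1 and 12.3 agree. The SAP softens the verb: "then trilaciclib or placebo + E/P may be continued for up to 4 cycles while the atezolizumab is held".

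**When atezolizumab is held.** The Synopsis says "Atezolizumab dosing will be held in the event of any irAEs attributed to atezolizumab until the event has improved to" Grade 1 or less.

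**Scope of study drug.** Section 8.2: "Study drug refers to trilaciclib or placebo + E/P/A during the induction part".

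**The concern.** Both rules can apply to one patient at one visit. While atezolizumab is on hold for a nonhematologic immune event that is still above Grade 1 and above the patient's baseline, the start criterion as worded is not met, yet another section says that E/P goes on. Up to 60 centers will read these sections, and two of them could treat the same event differently: one starts the next cycle on schedule, the other waits for recovery.

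The first stake is conduct: whether a patient with an active immune event receives chemotherapy should not depend on which section a site consults. The second is analysis. In SAP Section 5 a cycle ends on Day 1 of the next one, so the timing of later cycles sets the length of the induction period, and with it dose intensity and the per-week offsets.

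**Working it through.** The plan states no figure on this point, so there is none to reproduce. The check is a comparison of text, followed by simple arithmetic on what a delay does to the analysis.

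1. **Where the rules overlap.** The wait rule applies when a nonhematologic drug-related toxicity other than alopecia is above Grade 1 and above baseline. The continue rule applies when an immune-related event is attributed to atezolizumab and atezolizumab is held, which under the Synopsis lasts until Grade 1 or less. The overlap is a nonhematologic immune event above both Grade 1 and baseline. Events at Grade 1 or at baseline do not conflict.

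2. **Whether atezolizumab toxicity counts as drug-related.** The criterion does not say. Pointing towards yes:
   - 8.2 includes atezolizumab in study drug during induction.
   - 10.5.1 and 10.5.2 apply the 6.1.1 criteria in maintenance, when atezolizumab is the only drug given.
   - 10.3.2 and 10.3.3 put the allowance of up to 15 weeks for immune toxicity (12 for recovery + 3 for steroid taper = 15) in the same paragraph as the start criteria.
   - 8.4.5.2.1 (Other Toxicities) uses the narrower term chemotherapy-related, which the start criterion does not.

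3. **Which delay limit applies.** Mandatory discontinuation of E/P after more than 9 weeks is tied to toxicity of trilaciclib/placebo + E/P. The limit of 15 weeks ends only in stopping atezolizumab. An E/P delay caused solely by an atezolizumab event therefore has no mandatory stopping point, although a total E/P delay above 9 weeks must be discussed with the medical monitor (6.1.1).

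4. **Whether the SAP settles it.** No. Protocol Section 13 lets the SAP override the protocol only for differences in analyses, so the change from *will* to *may* does not decide conduct.

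5. **What a delay does to the analysis.** Illustration for one patient, assuming four cycles, a nominal 4 × 21 days = 84 days = 12 weeks, and the same events and doses whatever the delay. The ratio to the on-time per-week rate is 12 / (12 + d):
   - d = 3 weeks: 12/15 = 0.80
   - d = 6 weeks: 12/18 = 0.67
   - d = 9 weeks: 12/21 = 0.57

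   The weekly offset is used for RBC transfusion (SAP 6.2.7.1.2) and MAHE (SAP 6.2.7.2.1). Relative dose intensity (SAP 5.2.1.3) falls by the same factor. For etoposide at full dose, 4 × 300 = 1200 mg/m² is 100 mg/m²/week over 12 weeks (100%) and 80 over 15 weeks (80%). Occurrence of severe neutropenia, G-CSF use and all-cause dose reductions use the number of cycles as offset, which a delay alone does not change.

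6. **Cycle 1 duration of severe neutropenia.** The end-of-cycle date becomes the end date only if the episode is unresolved (SAP 5.1.1.2.1). Such a patient has ANC below 0.5 × 10⁹/L and already fails the start requirement of 1.5 × 10⁹/L, so the cycle waits under either rule. If a cycle is delayed for another reason, laboratory tests are still done on the scheduled Day 1 (Protocol 11.4.2).

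**The case against.** The best defence is that the specific rule overrides the general one. The continue rule addresses exactly this event, is in bold in 8.4.5.3 and appears five times in the protocol. The neighbouring text in 8.4.5.2 links cycle delay to the chemotherapy agents, and 6.1.1 speaks of meeting the continuation criteria only in the sentence on trilaciclib/placebo + E/P toxicity. That drug-related includes atezolizumab is an inference, since the criterion does not say study-drug-related and causality is judged for each drug (11.4.1.5). This reading is plausible, but it is nowhere stated, and the maintenance cross-reference and the 15-week allowance inside the cycle-start paragraph tell against it. Immune-event management is also referred to Appendix 1, whose content is not in the documents reviewed and may bear on this.

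The defence is right to limit the consequences. Three stronger readings are tempting and not supported:

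- **A patient count.** A reader might add the immune events in Protocol Table 4-1 (68+7+23+10+7+101+36+7+1+5 = 265 of 2160, 12.3%; 246, or 11.4%, after removing 19 patients counted twice for thyroid events) and infer about 12 of 106 patients. Those counts cover all grades and all treatment time in urothelial and lung cancer (NSCLC) patients, and part of the table is not in the text available. Thyroid events make up 137 of the 265. Only events before Cycle 4 Day 1 (3 × 21 days = 9 weeks) can delay an E/P cycle, whereas median onset of the commoner events is 3.5 to 5.5 months.
- **A delay as long as the planned induction.** The 12 weeks is the most allowed for recovery, not an expected E/P delay. Stated median durations for hepatitis, colitis and pneumonitis are 1, 1.4 and 1.5 months.
- **Damage to the Cycle 1 primary endpoint.** Step 6 of the working shows why this route largely closes.

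**Conclusion.** The contradiction stands for one defined case: a nonhematologic immune-related event attributed to atezolizumab, above Grade 1 and above baseline, when an induction cycle is due. The text then gives opposite instructions without stating precedence. This takes drug-related at face value, with no unwritten exception for atezolizumab.

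The number of patients affected is probably small and cannot be computed, because the documents give no rate of such events by grade within induction. The ratios of 0.80, 0.67 and 0.57 describe one patient under assumed delays, not a trial-level effect. Both arms receive atezolizumab under blinding, so the expected result is noise in induction duration, dose intensity and the per-week offsets; bias has not been shown. Of the endpoints in the SAP's multiplicity procedure, only RBC transfusion uses the weekly offset; MAHE is supportive in this SAP. Sample size and alpha are unaffected. The case for correction rests mainly on consistent conduct and patient safety.

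**What to change.** The sponsor should reconcile the wait rule (Synopsis, 6.1.1, 8.4.5.2, 10.3.2, 10.3.3 and the SAP's cycle criteria) with the continue rule (Synopsis, 6.1.1, 8.4.5.3, 10.3.4, 12.3 and the SAP). The start criterion should say whether toxicity attributed only to atezolizumab counts, and which delay limit then governs E/P. The same verb should appear in the protocol and the SAP. Which clinical rule applies is for the sponsor to decide.

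The cost is a clarifying sentence or two repeated in those sections, with no new data. Identifying delays caused only by immune events would be a separate and optional step, and it is not free: SAP 5.2.1.4 says that the reason for a cycle delay is not collected. It would need a new field, or derivation from the per-drug causality and action-taken data (Protocol 11.4.1.5 and 11.4.1.6).
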